12 SECONDARY OUTCOMES

12.1 Neratinib Treatment Patterns

Neratinib treatment patterns will be described as frequencies and percentages or summary statistics, as appropriate, for FAS and by subgroup EU label; Pathologic stage; Residual disease after neoadjuvant treatment; Risk profile; Previous adjuvant or neoadjuvant therapy and Prior transtuzumab-based regimen overall and last treatment (Section 8.4).

For duration of neratinib treatment calculations, the date of first and last neratinib administration will be taken from the eCRF “Neratinib Treatment” form, variables “Neratinib Initiation date” and “Definitive discontinuation date” respectively. Interruptions, compliance, and dose changes are not considered for duration of neratinib treatment.

Neratinib treatment initiation details:

- Time from breast cancer diagnosis to neratinib initiation (months), calculated as:
 - $(Date\ of\ first\ neratinib\ administration - Date\ of\ diagnosis + 1) / 30.4$
- Time from completion of adjuvant trastuzumab-based therapy to neratinib initiation (months), calculated as:
 - $(Date\ of\ first\ neratinib\ administration - Date\ of\ completion\ of\ adjuvant\ trastuzumab-based\ therapy + 1) / 30.4$
- Performance status scale used at neratinib initiation: ECOG, Karnofsky, Other
 - If ECOG: 0, 1, 2, 3, 4, Unavailable
 - If Karnofsky: 100, 90, 80, 70, 60, 50, 40, 30, 20, 10, Unavailable and 90-100, 70-80, 50-60, 30-40, 10-20, Unavailable
- Performance status computed ECOG score (based on Table 3): 0, 1, 2, 3, 4, Unavailable
- Duration of neratinib treatment (months), calculated as:
 - For discontinued treatment,
 $(Date\ of\ last\ administration - Date\ of\ first\ administration + 1) / 30.4$

Document: ZZA65950_NEAR_SAP_v2.0

Author: [name]

Version Number: 2.0

Version Date: 22SEP2023

- For ongoing treatment, (*EOB date - Start date + 1*)
- Duration of neratinib treatment (categorized): ≤ 3 months, > 3 months to < 12 months, 12 months, >12 months
- Initial daily dosage (mg)
- Initial daily dose (mg), category: 40mg, 80mg, 120mg, 160mg, 200mg, 240mg, ...; and <240mg, 240mg, >240mg

Treatment modifications (dosage changes):

- Number and percentage of patients with at least one neratinib treatment modification. Percentage computed among FAS.
- Number of temporary modifications by patient
- Temporary modifications per patient category: 1, 2, >2. Percentage computed among FAS patients with at least one neratinib treatment modification.

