- Number and percentage of patients by reasons reported for all treatment modifications: Worsening condition, Adverse event, Physician's decision, Patient's wish, Other. All dose changes will be captured in the CRF, therefore a patient can contribute to several reasons. Percentage computed among FAS patients with at least one neratinib treatment modification.
- Number and percentage of patients by reason for first treatment modification: Worsening condition, Adverse event, Physician's decision, Patient's wish, Other. All dose changes will be captured in the CRF, therefore a patient can contribute to several reasons.
- Number and percentage of patients by reason for subsequent treatment modifications⁽¹⁾: Worsening condition, Adverse event, Physician's decision, Patient's wish, Other. All dose changes will be captured in the CRF, therefore a patient can contribute to several reasons.
- Dose at first modification (mg)

- Dose at first modification (mg), category: 40mg, 80mg, 120mg, 160mg, 200mg, 240mg; and <240mg, 240mg, >240mg. Percentage computed among FAS patients with at least one neratinib treatment modification.
- Dose at subsequent modifications (mg)⁽¹⁾
- Dose at subsequent modifications (mg)⁽¹⁾, category: 40mg, 80mg, 120mg, 160mg, 200mg, 240mg; and <240mg, 240mg, >240mg. Percentage computed among FAS patients with the subsequent neratinib treatment modification.

⁽¹⁾Presented individually for each modification.

- Dose reduction at first modification: Yes, No. Percentage calculated among patients with at least one neratinib treatment modification.
 - Dose reduction⁽²⁾
 - Dose reduction⁽²⁾ category: 1 tablet, 2 tablets, > 2 tablets. Percentage calculated among patients with a reduction at first modification.
- Dose escalation at first modification*: Yes, No. Percentage calculated among patients with at least one neratinib treatment modification.
 - Dose escalation⁽²⁾
 - Dose escalation⁽²⁾ category: 1 tablet, 2 tablets, > 2 tablets. Percentage calculated among patients with an escalation at first modification.

⁽²⁾ 1 tablet of neratinib corresponds to 40 mg.

Temporary neratinib treatment discontinuations details:

- Number and percentage of patients with at least one temporary treatment discontinuation. Percentage computed among FAS.
- Number of temporary discontinuations by patient
- Temporary discontinuations per patient category: 1, 2, >2

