- Number and percentage of patients by reason for all temporary discontinuations: Worsening condition, Adverse event, Physician's decision, Patient's wish, Other. All temporary discontinuations will be captured in the CRF, therefore a patient can contribute to several reasons. If the same reason was reported several times for the same patient, the patient contributes only once to the reason. Percentage computed among FAS patients with at least one temporary neratinib treatment discontinuation.
- Number and percentage of patients by reason for first temporary discontinuation: Worsening condition, Adverse event, Physician's decision, Patient's wish, Other. All temporary discontinuations will be captured in the CRF, therefore a patient can contribute to several reasons. Percentage computed among FAS patients with at least one temporary neratinib treatment discontinuation.
- Number and percentage of patients by reason for subsequent temporary discontinuations⁽¹⁾: Worsening condition, Adverse event, Physician's decision, Patient's wish, Other. All temporary discontinuations will be captured in the CRF, therefore a patient can contribute to several reasons. Percentage computed among FAS patients with at least one temporary neratinib treatment discontinuation.
- Dose at first re-initiation (mg)
- Dose at first re-initiation (mg), category: 40mg, 80mg, 120mg, 160mg, 200mg, 240mg; and <240mg, 240mg, >240mg
- Dose at subsequent re-initiations (mg)⁽¹⁾
- Dose at subsequent re-initiations (mg)⁽¹⁾, category: 40mg, 80mg, 120mg, 160mg, 200mg, 240mg; and <240mg, 240mg, >240mg

⁽¹⁾Presented individually for each re-initiation.

- Duration of first treatment interruption (days), calculated as:
 - $(End\ date\ of\ the\ first\ neratinib\ treatment - Start\ date\ of\ first\ re-initiation + 1)$

- Duration of subsequent treatment interruptions (days)⁽²⁾, calculated as:
 - *(End date of the previous neratinib treatment – Start date of subsequent re-initiation + 1)*

⁽²⁾Presented individually for each treatment interruption.

Permanent neratinib treatment discontinuation:

- Number and percentage of patients who discontinued the treatment permanently. Percentage computed among FAS.
- Number and percentage of patients by duration of treatment before discontinuation: ≤ 3 months, > 3 months to < 12 months, 12 months and > 12 months. Percentage computed among FAS patients who discontinued neratinib treatment permanently.

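### SAP 12.1: the interruption formula never gives a positive length, ongoing neratinib duration is not converted to months, and the 12-month class is empty unless durations are rounded

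*SAP*

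**What the plan says.** Three rules in SAP 12.1 (Neratinib Treatment Patterns) are at issue.

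- **Interruption length, in days.** Subsequent interruptions are computed as "End date of the previous neratinib treatment – Start date of subsequent re-initiation + 1". The first interruption uses the same order: end of the first treatment period, minus first re-initiation, plus 1. The results are "Presented individually for each treatment interruption".
- **Treatment duration, in months.** For discontinued patients it is last minus first administration plus 1, divided by 30.4. For ongoing patients it is "EOB date - Start date + 1", with no divisor under the same heading. SAP 13.1 (First Recurrence) has the same pair of lines, also headed in months, for treatment given at first recurrence. In SAP 12.2 (Concomitant Treatments), the ongoing line for durations in months does carry the divisor.
- **Duration classes.** 12.1 plans "Duration of neratinib treatment (categorized): ≤ 3 months, > 3 months to < 12 months, 12 months, >12 months" and repeats the classes for permanent discontinuation: "duration of treatment before discontinuation: ≤ 3 months, > 3 months to < 12 months, 12 months and > 12 months". No rounding rule is stated.

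**The concern.** Interruptions and treatment duration are part of the first secondary objective, and Protocol 4.3.2 lists the duration of temporary discontinuation among the data to be collected. If 12.1 is programmed literally, interruption lengths come out zero or negative. Days for ongoing patients are averaged with months for everyone else. The class where a reader would look for patients who took the recommended one-year course (Protocol 2) either has nobody in it or has a membership set by an unstated rounding choice.

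The interruption formula also has more than one plausible repair, and the repairs disagree. Appendix 1 of the SAP lists a temporary discontinuation date but does not say whether it is the last day on drug or the first day off it.

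**Working it through.** The plan states no figure to reproduce here. The check evaluates the formulas as written.

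**Inputs.** Formulas and classes from SAP 12.1; cut-off 05 July 2022 (SAP 7.5); last permitted start 31 December 2020 (SAP 7.1); 120 patients (SAP 4.2).

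**1. Interruption length.** Let the last dose be on day d and the restart on day d + g + 1, so that g days are drug-free.

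- End date is the last dose: d - (d + g + 1) + 1 = -g.
- End date is the first day off drug: (d + 1) - (d + g + 1) + 1 = 1 - g.

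Example: last dose on day 100, restart on day 114, true gap 13 days.

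| Formula | End = last dose (100) | End = first day off (101) |
|---|---|---|
| SAP: end - restart + 1 | -13 | -12 |
| Dates swapped, +1 kept | 15 | 14 |
| Right formula for that date | 114 - 100 - 1 = 13 | 114 - 101 = 13 |

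Swapping the dates alone overstates the gap by 2 days or 1 day.

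**2. Ongoing treatment.** Without the divisor, every value is 30.4 times too large.

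- An ongoing patient with 13 days reads as 13 months and enters the over-12-months class; the true value is 13/30.4 = 0.43.
- A patient last seen on drug at day 100 reads as 100 instead of 100/30.4 = 3.3 months.
- A patient who started on 31 December 2020 and was still on drug at cut-off has 552 days inclusive. This reads as 552 instead of 552/30.4 = 18.2 months. The class is right but the value is not.
- Shift in the mean from one such patient among 120: (100 - 3.29)/120 = 0.8 months, or (552 - 18.16)/120 = 4.4 months.

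Wrong placement in the over-12-months class therefore concerns ongoing patients observed for 13 to 364 days. Longer ongoing durations belong there anyway if durations are unrounded.

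**3. The 12-month class.** 12 x 30.4 = 364.8 days, which is not a whole number. 364/30.4 = 11.974, 365/30.4 = 12.007 and 366/30.4 = 12.039.

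| Rounding of days/30.4 | Day counts that equal 12 |
|---|---|
| None | none |
| Two decimals | none |
| One decimal | 364 to 366 |
| Whole months | 350 to 379 |

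For whole months, 349 gives 11.48, 350 gives 11.51 and 379 gives 12.47. 380 gives exactly 12.5, taken here as rounding up to 13.

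**The case against.** The strongest defence is that these are clerical slips. If the end date is the last dose, the interruption formula has the right size and only the wrong sign, and negative lengths would be seen at the first output review. The months heading and the divisor one line above make the intent for ongoing patients clear. Few patients may be ongoing: the recommended course is one year, the cut-off is about 18 months after the last permitted start, and death is itself a listed reason for definitive discontinuation. A 12-month class between under 12 and over 12 is most naturally read in whole months, which gives a usable class. The table shells named in SAP 9 are not among the documents and may state the rounding.

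Most of this stands as a limit on weight. It does not make the two formulas right. An output review would catch the sign but not the plausible positive values that result from swapping the dates and leaving the +1. Ongoing patients can still arise, because SAP 7.8 ends observation at last contact if that is earlier. On rounding the defence is fair: the class is underspecified, and it is empty only if durations are left unrounded.

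A reader might infer that one-year completion cannot be recovered from the plan. The documents do not support that. 12.1 also plans Kaplan-Meier estimates of time to permanent discontinuation, including at 12 months, and lists end of the treatment period as a reason for stopping. Neither depends on the duration class.

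A reader might also infer that 12.1 fails by not summing dose or days off drug within a patient. It does not. The SAP says openly that "Interruptions, compliance, and dose changes are not considered for duration of neratinib treatment", and no objective asks for dose intensity. Dose, duration, discontinuations and reasons are what the protocol asks for, and 12.1 plans them.

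**Conclusion.** Two formulas are wrong as written and one class is underspecified. The interruption formula returns -g or 1 - g for every gap of g drug-free days, whichever date the eCRF records. The ongoing-treatment line returns days under a months heading, in 12.1 and again in 13.1. The 12-month class contains no whole day count under days/30.4 unless durations are rounded.

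These results are exact and rest only on the SAP's formulas. The effect on reported summaries is not known, because the documents do not give the number of interruptions or ongoing patients. The mean shifts of 0.8 and 4.4 months assume 120 patients and a single ongoing patient, and the true number may be zero. It would be too strong to say that the duration results will be materially inflated.

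The outputs are descriptive: secondary in 12.1 and exploratory in 13.1. The primary outcome is not touched, and the Kaplan-Meier outputs in 12.1 are not affected by the class definition. This is a minor correction, worth making because the SAP text is what the programmer follows.

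**What to change.** 1. **Interruptions, first and subsequent.** Compute re-initiation date minus last dose date minus 1. If the eCRF records the first day off drug, use re-initiation date minus that date. State in the SAP which date it is.
2. **Ongoing treatment.** Divide by 30.4 in both 12.1 and 13.1, as 12.2 already does for durations in months, and report the number of patients ongoing.
3. **Duration classes.** Define the 12-month class by a day window in both places in 12.1 and set the neighbouring classes to match. If whole months are meant: 350 to 379 days, with the lower neighbour ending at 349 and the upper starting at 380. If an exact year is meant: 364 to 366 days.

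The cost is a few lines of SAP text and programming, with no new data. If the database is already locked, Protocol 4.7.1 provides the route: describe the changes as deviations in the study or statistical report.

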7.7 Follow-up Period

The follow-up period for each patient extends from index date to end of the study observation period. Patients' data collection will be censored at date of death, or among patients who did not die, at the

end of the study observation period or at the date of last visit, whichever occurs first. Patients will have variable follow-up periods length, depending on their index date and last contact date.

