7.8 End of Observation (EOB) Date

The end of observation (EOB) date is defined as the study entry date, date of death or date of last contact, whichever happens first.

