- Number and percentage of patients by reason for definitive discontinuation: Disease recurrence, Adverse event, Patient's wish, Physician's decision, Patient death, End of treatment period, Other. Percentage computed among FAS patients who discontinued neratinib treatment permanently.
 - Number and percentage of patients by switch onto another treatment following definitive discontinuation: Yes, No. Percentage computed among FAS patients who discontinued neratinib treatment permanently.

To supplement descriptions of neratinib treatment patterns for FAS, the Kaplan-Meier and reverse Kaplan Meier methods will be used. For Kaplan Meier, the number of events, number of censored data, median survival estimates will be reported along with the 1st and 3rd quartiles, and the corresponding two-sided 95% CI. Estimates of the proportion of patients not presenting the event of interest at 3-month intervals (1, 3, 6, 9, 12, 15, 18 months) and the corresponding two-sided 95% CIs. For the reverse Kaplan Meier, the number of events, number of censored data points, median follow-up time, Q1 and Q3 follow-up time and corresponding two-sided 95% CI will be presented. Kaplan Meier and reverse Kaplan Meier methods will be used for the following outcomes:

Document: ZZA65950_NEAR_SAP_v2.0

Author: [name]

Version Number: 2.0

Version Date: 22SEP2023

- Time from neratinib initiation to first temporary discontinuation (treatment persistence)
- Time from neratinib initiation to permanent treatment discontinuation⁽¹⁾
- Time from neratinib initiation to first treatment modification

⁽¹⁾ For the analysis of time to permanent discontinuation, death will be considered as an event.

Additionally, the Kaplan-Meier and reverse Kaplan Meier analysis will also be performed for permanent treatment discontinuation by subgroups Concomitant Prophylaxis Antidiarrheal and Initial Dose of Neratinib (section 8.4).

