Appendix 1. Partial Date Conventions

No imputation of missing data will be performed; missing data will not be replaced in this study, unless specified and for the following dates (Table 8). Imputed dates will not be presented in the listings.

Table 8 Missing data imputation rules

Variable	Rule
General rule for partial dates	If the day of event is missing and month and year are available: the day will be imputed to the first day of the month, in case of a start date, and to the last day of the month, in case of an end date. Unless such imputation is illogical. If the day and month are missing, the date will not be imputed.
Date of abstraction	Will not be imputed
Date of informed consent/ non-opposition	Will not be imputed
Date of primary diagnosis of Breast Cancer	General rule for partial dates applies.
Date of pregnancy	Will not be imputed
Start date (Pre-/Post-surgery neoadjuvant therapy)	Will not be imputed.
End date (Pre-/Post-surgery neoadjuvant therapy)	Will not be imputed.
Date of surgery	Will not be imputed.
Date of radiotherapy	Will not be imputed.
Date of weight measurement	General rule for partial dates applies.
Date of performance status assessment (follow-up)	Will not be imputed.
Neratinib initiation date	General rule for partial dates applies.

Variable	Rule
Neratinib definitive discontinuation Date	General rule for partial dates applies.
Treatment modification date	Will not be imputed.
Treatment temporary discontinuation date	Will not be imputed.
Treatment date of re-initiation	Will not be imputed.
Concomitant treatment start date	General rule for partial dates applies.
Concomitant treatment end date	General rule for partial dates applies.
Start date of AE	General rule for partial dates applies.
Date of death	General rule for partial dates applies.
Admission date (Hospitalization due to AE)	Will not be imputed.
Discharge date (Hospitalization due to AE)	Will not be imputed.
Date of recurrence (AE recurrence)	Will not be imputed.
Date of recovery (AE outcome)	Will not be imputed.
Date of first breast cancer recurrence	General rule for partial dates applies.
Treatment start date (Breast cancer recurrence)	General rule for partial dates applies.
Treatment end date (Breast cancer recurrence)	General rule for partial dates applies.
Date of last contact	General rule for partial dates applies.
Date of consent withdrawn	Will not be imputed.

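### SAP 12.1 calls time to first temporary discontinuation 'treatment persistence', so a permanent stop or death without an earlier pause is not an event, and no rule says when the risk period ends

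*SAP*

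**What the plan says.** Protocol (Synopsis, 4.3.2, 4.7.2) names treatment persistence as a Kaplan-Meier output, listed beside median time to permanent discontinuation and median time to first modification. It does not define persistence. SAP 7.10, which lists changes from the protocol, does not mention it.

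SAP 12.1 supplies the definition in a list of three Kaplan-Meier outcomes. The first is "Time from neratinib initiation to first temporary discontinuation (treatment persistence"). The other two are time to permanent discontinuation and time to first treatment modification. A footnote marked on the permanent-discontinuation line only reads "For the analysis of time to permanent discontinuation, death will be considered as an event".

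The two kinds of stop are kept apart throughout:
- They have separate tables: "Number and percentage of patients with at least one temporary treatment discontinuation" and "Number and percentage of patients who discontinued the treatment permanently".
- They have separate date variables in Appendix 1, Table 8: "Neratinib definitive discontinuation Date", which follows the general imputation rule, and "Treatment temporary discontinuation date", which is not imputed.

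On the risk period, 12.1 gives no censoring rule. Section 8.2 refers to 13.2, where patients without the event are censored at the last date known alive, or at study entry date if alive at study end. Section 7.7 says "The follow-up period for each patient extends from index date to end of the study observation period", and 7.8 has end of observation "defined as the study entry date, date of death or date of last contact, whichever happens first". Estimates are to be reported at 1, 3, 6, 9, 12, 15 and 18 months.

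**The concern.** A reader will take treatment persistence to mean either that the patient is still on the drug or that use has been uninterrupted. The SAP event matches neither. Someone who stops for good at month 2 without a pause never counts as an event. Someone who pauses for a few days and completes the course does. Early permanent stops are foreseen: 12.1 tabulates stops at up to 3 months and between 3 and 12 months.

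The second gap is the risk period. If the first-pause and first-modification curves are run to end of observation, patients who have taken their last dose stay in the risk set for an event they can no longer have. At 15 and 18 months the estimate would then mostly restate the proportion who ever paused. Section 12.1 also asks for reverse Kaplan-Meier follow-up on these outcomes, and that depends directly on the unstated censoring date. Two programmers could report different results from the same data.

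At stake is a named, descriptive secondary outcome that may be published under a label it does not fit.

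**Working it through.** The plan states no persistence figure, so there is none to reproduce. Pause and stop rates are not in the documents. All rates and timings below are assumptions, chosen to show the mechanism at the SAP's n = 120 (4.2).

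**1. Potential follow-up.** The last index date is 31 December 2020 (7.1) and the common cut-off is 05 July 2022 (7.5). With the SAP formula, (551 + 1)/30.4 = 18.2 months. Every patient could therefore be followed past the 18-month landmark, barring death or loss. Protocol section 2 and SAP 11.1 refer to a one-year course.

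**2. Event definition.** Assume 48 patients stop permanently at month 2, 12 pause briefly at month 1 and complete at month 12, and 60 complete without a pause. Let k of the 48 stoppers have paused briefly at month 1 first. All pauses end before month 6, and there are no deaths or losses.

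- Still on neratinib at 6 months: (12 + 60)/120 = 60%.
- Uninterrupted use at 6 months: 60/120 = 50%.
- SAP 'persistence': 1 − (12 + k)/120.

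| k | SAP figure | minus on-drug share | minus uninterrupted share |
|---|---|---|---|
| 0 | 90% | +30 points | +40 points |
| 24 | 70% | +10 | +20 |
| 36 | 60% | 0 | +10 |
| 48 | 50% | −10 | 0 |

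Reverse mix: 12 stoppers, 48 pausing completers and 60 others. On drug = 108/120 = 90%; uninterrupted = 60/120 = 50%. SAP figure = 1 − (48 + k)/120 = 60%, 55% or 50% for k = 0, 6 or 12. Here it understates the on-drug share by 30 to 40 points.

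One relation is general. The first-pause curve is never below the curve for first stop of either kind, and equals it only when nobody stops without an earlier pause.

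**3. Response to more early stopping.** Assume independent exponential times to first pause and to early permanent stop, with the end-of-observation default. Fix the 12-month pause risk at 20%. With hazards proportional to a = −ln(0.8) = 0.223 and b, the proportion paused by month 12 is a/(a + b) × (1 − e^−(a+b)).

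- Early-stop risk 20% (b = 0.223): 0.5 × (1 − 0.64) = 0.180, so SAP 'persistence' is 82.0%, with 80% not yet stopped.
- Early-stop risk 60% (b = 0.916): 0.196 × (1 − 0.32) = 0.133, so SAP 'persistence' is 86.7%, with 40% not yet stopped.

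In this scenario the SAP figure rises as more patients stop for good.

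**4. Risk period.** Return to the first cohort, but let the 12 completers pause at month 4. The 6-month estimates are:

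- k = 0: stoppers censored at last dose, 1 − 12/72 = 83%; end-of-observation default, 1 − 12/120 = 90%.
- k = 24: last dose, 0.8 × (1 − 12/72) = 67%; default, 0.8 × (1 − 12/96) = 70%.

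At months 15 and 18 all 120 have ended treatment. The default still reports 90% with 108 at risk (k = 0), 70% with 84 (k = 24) or 50% with 60 (k = 48). With censoring at last dose, nobody is at risk.

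**The case against.** Several points against this have force.

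- **The documents are silent on the risk period; they do not direct it past the last dose.** A reader might infer that the SAP orders patients to stay at risk after stopping. It does not say so. The 13.2 rule is written for the outcomes in its own subsections, 7.7 and 7.8 define follow-up rather than a risk set for these curves, and the table shells mentioned in SAP section 9, which are not among the documents, may carry a note. What stands is that no rule is stated, and the only written defaults run to end of observation.
- **The protocol left persistence undefined, and the SAP prints its definition beside the label.** A reader of 12.1 is told what is estimated. A reader of a results table or abstract may not be, and no ordinary meaning of the word fits the event.
- **The illustrations are constructed.** The gaps follow from the chosen rates. They show that the figure can err in either direction against the on-drug share, not that it will in this study.
- **Most patients being off drug at 15 and 18 months is an inference.** It rests on the one-year course. SAP 12.1 allows for treatment beyond 12 months and for ongoing treatment.
- **Making permanent discontinuation the event raises its own question.** The reasons for definitive discontinuation in 12.1 include reaching the end of the treatment period. Unless this is addressed, planned completers become non-persistent at about month 12. This stands, and the fix must cover it.
- **The information survives.** The permanent-discontinuation curve, duration bands and reasons are all reported. That limits the harm but does not correct the label.

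**Conclusion.** The point on the label and event definition holds on the text alone. As written, a permanent stop or death on treatment without an earlier pause is not an event. The figure is not the share still on neratinib, and it is the share with uninterrupted use only if every permanent stopper paused first. On the risk period, the finding is an unstated rule for the first-pause and first-modification curves. If the written defaults were applied, patients would remain at risk after their last dose, with most effect at 15 and 18 months.

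The size in this study cannot be given. On the assumed cohorts, the gap against the on-drug share runs from +30 to −40 points. A reader might infer that persistence will be overstated; the documents do not support a direction, since it depends on pause rates, stop rates and their overlap.

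This should be fixed, but it is a correction to one descriptive secondary outcome. It affects no test and no sample size.

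**What to change.** In SAP 12.1:

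- (a) Rename the present curve 'time to first temporary discontinuation'.
- (b) Report 'treatment persistence' with permanent discontinuation or death as an event. Take it either from the existing permanent-discontinuation curve (still on neratinib) or as first stop of either kind (uninterrupted use), and state which.
- (c) State whether definitive discontinuation at the end of the planned treatment period is an event, is censored, or truncates the curve. Present the 15- and 18-month estimates accordingly.
- (d) For the first-pause and first-modification curves, end the risk period at permanent discontinuation, by censoring or as a competing event. State which, and state how death on treatment is handled.
- (e) If first stop of either kind is used, state how partial dates are handled, because Table 8 imputes definitive but not temporary discontinuation dates.

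The cost is SAP wording and programming. The temporary and definitive discontinuation dates and the death date are already collected. Protocol 4.7.1 allows a SAP amendment before database lock; after lock, the change would be reported as a deviation.
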